### **6.6.1.3 Within participant dose modification in Part A1**

Dose adjustments and/or changes in dosing schedule are not permitted.

## 6.6.2 Part B

The justification for the UCB6114 start dose for Part B is presented in Section 4.3.3.2.1.

In Part B, the decision to proceed to the next dose level (either an escalation or a de-escalation) will be made by the SMC as described in Section 4.1.4.1. Further data obtained from any previous dose level may also contribute to this decision.

The planned dose escalation scheme is given in Section 6.6.2.1.

### 6.6.2.1 Dose escalation scheme

A summary of the planned UCB6114 dose levels for dose escalation in Part B is provided in Table 6-7.

**Table 6-7: Dose escalation steps and justification (Part B)**

Dose Level	Dose (mg)	Justification
1	500	The starting dose selected for Part B is the Part A Cohort 3 dose (anticipated to be 500mg Q2W iv); see Section 4.3.3.1 for details.
2	1000	
The lowest dose to show a qualitative improvement in survival in the ApcMin;Vil1-Grem-1 model was 15mg/kg of Ab7326 mIgG1 administered BIW sc as monotherapy from an age of 21 days. A dose of 1000mg Q2W iv is expected to provide similar exposure in humans.
 
A dose of 1000mg is expected to provide an exposure approximately 50% of that given in combination with 5-fluorouracil where survival relative to either monotherapy was increased in the ApcMin;Vil1-Grem-1 model when dosing from an age of 35 days (30mg/kg BIW sc [for 6 weeks followed by 30mg/kg QW thereafter]).

3	2000	
A dose of 2000mg is expected to provide the same exposure in humans as that given in combination with 5-fluorouracil where survival relative to either monotherapy was increased in the ApcMin;Vil1-Grem-1 model when dosing from an age of 35 days.
 
In a separate study where Ab7326 mIgG1 was administered as monotherapy from an age of 21 days, no difference was observed between 30 and 60mg/kg BIW sc in the ApcMin;Vil1-Grem-1 model, and therefore, higher doses of UCB6114 are likely not warranted.

BIW=twice weekly; h=hour; iv=intravenous(ly); PK=pharmacokinetic(s); Q2W=every 2 weeks;  
sc=subcutaneous(ly)

### 6.6.2.2 UCB6114 dose modifications

Study participants who experience Grade 4 (life-threatening) nonhematologic toxicity, including diarrhea and mucositis, which is at least possibly related to UCB6114, will be discontinued from treatment.

Treatment with UCB6114 may temporarily be suspended for up to 3 weeks beyond the scheduled treatment day until toxicities are resolved to CTCAE Grade 2 or less. If UCB6114 is

held for more than 3 weeks beyond the scheduled treatment day, then the participant will be discontinued from treatment and will be followed up for safety and efficacy per the Schedules of Activities for Part A ([Table 1-4](#)), Part B ([Table 1-7](#)), and Part C ([Table 1-8](#)).

For permitted adjustments of the infusion rate in case of AEs refer to the IMP Handling Manual. Participants who experience severe or life-threatening infusion-related events (CTCAE Grade 3 or 4) will not receive further infusions. Hypersensitivity/infusion-related events should be managed per institutional guidelines. Premedication with steroids may be administered at the discretion of the investigator.

#### 6.6.2.3 TFD/TPI dose modifications

Dose modifications for TFD/TPI-related AEs are allowed as described below. A maximum of 3 dose reductions are permitted to a minimum of 20mg/m^2/dose.

Participants who permanently discontinue TFD/TPI treatment due to TFD/TPI-related toxicity will have the option to continue treatment with UCB6114 alone if, in the view of the investigator, the participant is deriving benefit.

In the case of hematological toxicities, TFD/TPI treatment may be interrupted or resumed according to the criteria stated in [Table 6-8](#). In the case of hematological and nonhematological toxicities, the dose may be modified according to the criteria stated in [Table 6-9](#). Reductions will be made in accordance with BSA ([Table 6-10](#)).

**Table 6-8: TFD/TPI dose interruption and resumption criteria for hematological toxicities**

Parameter	Interruption criteria	Resumption criteria a
Neutrophils	<0.5x10  /L	≥1.5x10  /L
Platelets	<50x10  /L	≥75x10  /L

TFD/TPI=trifluridine/tipriacil

a Resumption criteria applied to the start of the next cycle for all participants regardless of whether the interruption criteria were met.

**Table 6-9: TFD/TPI dose modifications in case of hematological and non-hematological toxicities**

Adverse reaction	Recommended dose modifications
Febrile neutropenia, CTCAE Grade 4 neutropenia (<0.5x10  /L) or thrombocytopenia (<25x10  /L) that results in more than 1 week's delay in start of next cycle. CTCAE Grade 3 or Grade 4 nonhematologic AEs; except for Grade 3 nausea and/or vomiting controlled by antiemetic therapy or diarrhea responsive to antidiarrheal medicinal products.	Interrupt dosing until toxicity resolves to Grade 1 or baseline. When resuming dosing, decrease the dose level by 5mg/m  /dose from the previous dose level ( Table 6-10 ). Dose reductions are permitted to a minimum dose of 20mg/m  /dose bid. Do not increase dose after it has been reduced.

AE=adverse event; bid=twice daily; CTCAE= Common Terminology Criteria for Adverse Events; TFD/TPI=trifluridine/tipriacil

**Table 6-10: TFD/TPI dose reductions according to body surface area**

Reduced dose	BSA (m  )	Dose (mg)	Tablets per dose		Total daily dose (mg)
			15mg/6.14mg	20mg/8.19mg	
Level 1 dose reduction: from 35mg/m  to 30mg/m 					
30mg/m 	<1.09	30	2	0	60
	1.09 to 1.24	35	1	1	70
	1.25 to 1.39	40	0	2	80
	1.40 to 1.54	45	3	0	90
	1.55 to 1.69	50	2	1	100
	1.70 to 1.94	55	1	2	110
	1.95 to 2.09	60	0	3	120
	2.10 to 2.28	65	3	1	130
	≥2.29	70	2	2	140
Level 2 dose reduction: from 30mg/m  to 25mg/m 					
25mg/m 	<1.10	25 a	2 a	1 a	50 a
	1.10 to 1.29	30	2	0	60
	1.30 to 1.49	35	1	1	70
	1.50 to 1.69	40	0	2	80
	1.70 to 1.89	45	3	0	90
	1.90 to 2.09	50	2	1	100
	2.10 to 2.29	55	1	2	110
	≥2.30	60	0	3	120
Level 3 dose reduction: from 25mg/m  to 20mg/m 					
20mg/m 	<1.14	20	0	1	40
	1.14 to 1.34	25 a	2 a	1 a	50 a
	1.35 to 1.59	30	2	0	60
	1.60 to 1.94	35	1	1	70
	1.95 to 2.09	40	0	2	80
	2.10 to 2.34	45	3	0	90
	≥2.35	50	2	1	100

BSA=body surface area; TFD/TPI=trifluridine/tipriacil

a At a total daily dose of 50mg, study participants should take 1x20mg/8.19mg tablet in the morning and 2x15mg/6.14mg tablets in the evening.

### 6.6.3 Part C

The justification for the UCB6114 start dose for Part C is presented in Section 4.3.3.2.2.

In Part C, the decision to proceed to the next dose level (either an escalation or a de-escalation) will be made by the SMC as described in Section 4.1.5.1). Further data obtained from any previous dose level may also contribute to this decision.

The planned escalation scheme is given in Section 6.6.3.1.

#### 6.6.3.1 Dose escalation scheme

A summary of the planned UCB6114 dose levels for dose escalation in Part C is provided in Table 6-11.

**Table 6-11: Dose escalation steps and justification (Part C)**

Dose Level	Dose (mg)	Justification
1	500	The starting dose selected for Part C is the Part A Cohort 3 dose (anticipated to be 500mg Q2W iv); see Section 4.3.3.1 for details.
2	1000	
The lowest dose to show a qualitative improvement in survival in the ApcMin;Vil1-Grem-1 model was 15mg/kg of Ab7326 mIgG1 administered BIW sc as monotherapy from an age of 21 days. A dose of 1000mg Q2W iv is expected to provide similar exposure in humans.
 
A dose of 1000mg is expected to provide an exposure approximately 50% of that given in combination with 5-fluorouracil where survival relative to either monotherapy was increased in the ApcMin;Vil1-Grem-1 model when dosing from an age of 35 days (30mg/kg BIW sc [for 6 weeks followed by 30mg/kg QW thereafter]).

3	2000	
A dose of 2000mg is expected to provide the same exposure in humans as that given in combination with 5-fluorouracil where survival relative to either monotherapy was increased in the ApcMin;Vil1-Grem-1 model when dosing from an age of 35 days.
 
In a separate study where Ab7326 mIgG1 was administered as monotherapy from an age of 21 days, no difference was observed between 30 and 60mg/kg BIW sc in the ApcMin;Vil1-Grem-1 model, and therefore, higher doses of UCB6114 are likely not warranted.

BIW=twice weekly; h=hour; iv=intravenous(ly); PK=pharmacokinetic(s); Q2W=every 2 weeks;  
sc=subcutaneous(ly)

#### 6.6.3.2 UCB6114 dose modifications

Study participants who experience Grade 4 (life-threatening) nonhematologic toxicity, including diarrhea and mucositis, which is at least possibly related to UCB6114, will be discontinued from treatment.

Treatment with UCB6114 may temporarily be suspended for up to 3 weeks beyond the scheduled treatment day until toxicities are resolved to CTCAE Grade 2 or less. If UCB6114 is

held for more than 3 weeks beyond the scheduled treatment day, then the participant will be discontinued from treatment and will be followed up for safety and efficacy per the Schedule of Activities.

For permitted adjustments of the infusion rate in case of AEs, refer to the IMP Handling Manual. Participants who experience severe or life-threatening infusion-related events (Grade 3 or 4) will not receive further infusions. Hypersensitivity/infusion-related events should be managed per institutional guidelines. Premedication with steroids may be administered at the discretion of the investigator.

#### 6.6.3.3 mFOLFOX6 dosing

Please refer to the individual package inserts for details on formulations and storage.

Antiemetic premedication prior to administration of chemotherapy is recommended and sites should follow their institutional standard of care.

The recommended administration of mFOLFOX6 is shown in [Table 6-12](#).

**Table 6-12: mFOLFOX6 dosing**

Drug	Dose	Administration
Oxaliplatin a	85mg/m 	iv in 250 to 500mL glucose 5% over 2 hours
Leucovorin a	400mg/m 	iv in 250mL glucose 5% over 2 hours
5-Fluorouracil	400mg/m 	iv bolus
5-Fluorouracil	2400mg/m 	iv over 46 hours via an infusor

mFOLFOX6=leucovorin 400mg/m^2 on Day 1, 5-fluorouracil 400mg/m^2 on Day 1 + 1200mg/m^2/day on Day 1 and Day 2, and oxaliplatin 85mg/m^2 on Day 1; iv=intravenous(ly)

a Oxaliplatin and leucovorin may be infused over the same two-hour period by using a Y-site connector placed immediately before the infusion site.

Within the study, mFOLFOX6 is administered every 14 days in 28-day treatment cycles up to a maximum of 6 cycles.

#### 6.6.3.4 mFOLFOX6 dose modifications

Dose modifications for mFOLFOX6-related AEs are allowed as described below. A maximum of 2 dose level reductions are permitted.

Participants who permanently discontinue treatment (all or individual drugs of the mFOLFOX6 regimen) due to toxicity will be considered for continuation of treatment with UCB6114 if, in the view of the investigator, the participant is deriving benefit.

Dose levels for individual drugs are as follows:

- Oxaliplatin:
  - Starting dose: 85mg/m^2
  - Dose Level -1: 65mg.m^2
  - Dose Level -2: 50mg/m^2
- 5-fluorouracil iv bolus:

- Starting dose: 400mg/m^2
- Dose Level -1: 320mg/m^2
- Dose Level -2: 200mg/m^2
- 5-fluorouracil infusion over 46 hours:
  - Starting dose: 2400mg/m^2
  - Dose Level -1: 2000mg/m^2
  - Dose Level -2: 1600mg/m^2

No dose adjustments are required for leucovorin.

#### 6.6.3.4.1 Dose modifications for neurological toxicity

If neurological symptoms (ie, paresthesia, dysesthesia) occur, oxaliplatin dosage adjustments should be made as outlined in [Table 6-13](#). No dose adjustments of 5-fluorouracil are recommended for neurotoxicity.

**Table 6-13: Dose modification for oxaliplatin-related neurological toxicity**

CTCAE (v5.0) Toxicity grade	Duration of toxicity	
	Transient (≥1 day and ≤14 days)	Persistent (present at start of next treatment)
1	Maintain dose level	Maintain dose level
2	Maintain dose level	Reduce 1 dose level
3	1 st time: reduce one dose level 2 nd time: reduce one dose level	Discontinue
4	Discontinue	Discontinue

CTCAE=Common Terminology Criteria for Adverse Events

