**Table 1-8: Schedule of Activities for Part C**

Procedure	Screening		Treatment				SFU Visit Within 30 days after final dose	Final Visit 3 months after final dose
	-28 to -1	-14 to -1	Cycle 1 & Cycle 2 (28 days)		Cycle 3 onwards (28 days)			
Cycle day			1	8	15	22	1	15
Informed consent a	X							
Eligibility assessment b	X	X	X g					
Demographic data and height	X							
Medical/surgical/cancer history/concomitant disease and current medical status	X		X g					
ECG c		X	X		X		X	X
Pregnancy test, if applicable		X d	X			X		X
UCB6114 administration			UCB6114 is administered as an iv infusion on Days 1 and 15 of each cycle					
mFOLFOX6 administration			mFOLFOX6 is administered iv starting on Days 1 and 15 of each cycle e					
Physical examination and weight f		X	X	X g	X	X g	X	X
Vital signs (BP, HR, RR, and temperature) h	X	X	X g	X	X g	X	X	X
ECOG performance status	X	X	X g	X	X g	X	X	X
Urinalysis i	X	X		X	X	X		X
Urinalysis for urinary markers of bone turnover			X		X		X	
Blood collection for serum markers of bone turnover			X		X		X	
Hematology k	X	X	X	X	X	X	X	X
Blood chemistry l	X	X	X	X	X	X	X	X
Coagulation m	X	X		X g		X		X
Blood collection for immunogenicity (ADA)			X			X p		X
Blood collection for circulating gremlin-1 analysis	X	X o	X o, q		X q		X p,q	X
Blood collection for genetic analysis	X	X o						
Blood collection for ctDNA analysis	X	X o	X o		X		X	

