## DLT Evaluatable Set

The DLT Evaluatable Set (DES) will include all study participants who, during the DLT assessment period:

- Receive the planned dose of UCB6114 (Part A and Part A1)
- Receive the planned dose of UCB6114 and at least 80% of the planned dose of TFD/TPI (Part B)
- Receive the planned dose of UCB6114 and at least 80% of the planned dose of mFOLFOX6 (Part C)
- Stopped treatment because of a DLT (any part of the study)

The DES will be used by the SMC for all dose escalation/de-escalation decision making.

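### On a 14-day schedule the two duration columns of Table 6-13 overlap and leave a gap, so some Grade 2 and Grade 3 neurotoxicity has two different oxaliplatin instructions, or none

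*Protocol*

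**What the plan says.** Protocol Section 6.6.3.4.1 sends the investigator to one table when paresthesia or dysesthesia occurs: "oxaliplatin dosage adjustments should be made as outlined in" Table 6-13. The table has one row per CTCAE grade and two columns under a common duration header. The first column is "Transient (≥1 day and ≤14 days" and the second is "Persistent (present at start of next treatment".

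The cells read, in substance:

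| Grade | Transient column | Persistent column |
|---|---|---|
| 1 | keep the dose | keep the dose |
| 2 | keep the dose | "Reduce 1 dose level" |
| 3 | down one level, first and second time | stop |
| 4 | stop | stop |

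On timing, the text under Table 6-12 states that "mFOLFOX6 is administered every 14 days in 28-day treatment cycles", and the Part C Schedule of Activities (Table 1-8) states that "mFOLFOX6 is administered iv starting on Days 1 and 15 of each cycle". A note to Table 1-8 allows a visit window of 2 days either way. Tables 6-14 and 6-15 allow treatment to be held for up to 2 weeks for other toxicities.

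**The concern.** The two columns use different criteria. The first asks how long the event lasts and does not require that it has ended before the next dose. The second asks only whether the event is there when the next treatment begins and sets no minimum length. With a dosing interval of 14 days and an upper bound of 14 days, one event can satisfy both. Neither Section 6.6.3.4.1 nor the table says which column then governs.

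What is at stake is consistent dosing of a neurotoxic background drug across sites. Two investigators with the same Grade 3 event in front of them could read the same table and either lower the dose or stop the drug.

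**Working it through.** The plan gives no figure to reproduce here. The check is whether the two definitions divide events cleanly on the stated schedule.

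**Inputs.** Dose on Day 1 and next dose on Day 15 (Table 1-8; text under Table 6-12). Transient: duration from 1 to 14 days. Persistent: present on the day of the next dose (both Table 6-13). The protocol does not say how days are counted, so both conventions are used: elapsed (last day minus onset day) and inclusive (the same plus 1).

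**Overlap, next dose on time.** An event with onset on Day d that is present on Day 15 has by then lasted 15 − d days elapsed, or 16 − d inclusive. For d = 2 to 14 this gives 13 down to 1 elapsed, or 14 down to 2 inclusive. All lie within the 14-day bound. For d = 1 it gives 14 elapsed (inside the bound) or 15 inclusive (outside). So when the Day 15 decision is made, every event with onset on Days 2 to 14 that is still present fits both headings under either count. A Day 1 onset does so only under the elapsed count.

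Judged by final duration, the overlap is smaller but remains. The last day present must be Day 15 or later, and at most d + 13 (inclusive) or d + 14 (elapsed). Summed over onset Days 1 to 14, that is 0 + 1 + … + 13 = 91 onset/end-day combinations inclusive, or 1 + 2 + … + 14 = 105 elapsed. These counts show that the overlap is not a single edge case; they are not probabilities.

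**Gap, next dose delayed.** Counting inclusively, an event of more than 14 days that has ended before the next dose meets neither definition. With the dose on Day 22 there are 7 + 6 + … + 1 = 28 such combinations. With the dose on Day 29 there are 14 + 13 + … + 1 = 105. A formal hold is not needed if the 2-day visit window applies to dosing visits, as the fourth example shows.

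| Onset | Last day present | Next dose | Duration (elapsed / inclusive) | Transient | Persistent |
|---|---|---|---|---|---|
| Day 5 | Day 9 | Day 15 | 4 / 5 | yes | no |
| Day 10 | Day 16 | Day 15 | 6 / 7 | yes | yes |
| Day 10 | Day 30 | Day 15 | 20 / 21 | no | yes |
| Day 1 | Day 16 | Day 17 | 15 / 16 | no | no |
| Day 1 | Day 20 | Day 22 | 19 / 20 | no | no |

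**Consequence.** Because the columns agree at Grades 1 and 4, the choice of column changes the instruction only at Grades 2 and 3.

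**The case against.** The best defence is that the intent can be read from the labels. Transient and persistent are ordinary contraries, 14 days is one dosing interval, and the natural sense is an event that came and went between doses against one still there at the next. An event present at the decision also has no final length yet, so it could be said not to be transient so far. For onset on Day 1 with inclusive counting and no delay, the two columns are in fact exact complements.

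Much of this stands. The reading is plausible, and many investigators would adopt it. But the protocol does not state it, and the printed 14-day bound works against it: a reader who applies the number to an event that began on Day 10 reaches the first column. It also does not say what to do once the next dose is delayed and the 14-day bound no longer matches the dosing interval. The gap is the rarer problem. It needs a long-lasting event together with a delay, through a hold for another toxicity or the visit window.

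A reader might also infer that the choice of column decides who counts in the mTPI decisions, since the DLT Evaluatable Set requires a participant to "Receive the planned dose of UCB6114 and at least 80% of the planned dose of mFOLFOX6 (Part C". The protocol does not support this. The limit is set on the regimen and no per-drug limit is given. If oxaliplatin alone were omitted on Day 15, the Cycle 1 share of mFOLFOX6 would be (0.5 + 1 + 1)/3 = 83% averaged over three drugs. With the 5-fluorouracil bolus and infusion taken separately it would be (0.5 + 1 + 1 + 1)/4 = 87.5%. By total mg/m² the plan is 2 × (85 + 400 + 400 + 2400) = 6570, and (6570 − 85)/6570 = 98.7%. All exceed 80%, so the participant is evaluable whichever column is read. Section 10.6 likewise ties nonevaluability to missed UCB6114 doses.

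**Conclusion.** The point holds as a wording defect. Read literally, Table 6-13 gives two different oxaliplatin instructions for a Grade 2 or Grade 3 event that starts between doses, is still present at the next dose and has lasted 14 days or less. It gives none for an event of more than 14 days that resolves before a delayed dose. Overlap on an on-time schedule arises under either way of counting days, for onset on Days 2 to 14.

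Its size is limited. Events that resolve before an on-time next dose fall only in the first column, and events present at the next dose whose final length exceeds 14 days fall only in the second. A reader might call the paired instructions opposite. They are not: keep against reduce, and reduce against stop, are successive steps of strictness. No endpoint, DLT definition, escalation table or sample size is shown to change. The case for acting is consistent, safety-relevant dosing across sites, above all at Grade 3. How often such events would occur cannot be judged from the protocol.

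**What to change.** The sponsor should reconcile the two column definitions of Table 6-13 so that every event falls in exactly one column, both when the next mFOLFOX6 dose is on time and when it is delayed by a hold or the visit window. The revised text should make clear where an event of 14 days or less that is still present at the next treatment belongs, where an event of more than 14 days that has resolved before a delayed treatment belongs, and how days are counted. Which instruction goes with which event is a clinical decision for the sponsor, and no view is taken on it here.

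The cost is a rewording of two column headings, perhaps with one sentence in Section 6.6.3.4.1. Nothing in the design, the data collected or the analysis needs to change.

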#### 6.6.3.4.2 Dose modifications for hematological toxicity

Recommended dose modifications for oxaliplatin and 5-fluorouracil for hematological toxicity are outlined in [Table 6-14](#).

**Table 6-14: Dose modification for hematological toxicity**

Prior to Dosing (Day 1 or Day 15)	Toxicity		Dose level for subsequent cycles	
	CTCAE (V5.0) Toxicity Grade	ANC (x10  /L)	Oxaliplatin	5-Fluorouracil
If ANC <1.2 on Day 1 or Day 15, hold treatment and perform weekly blood counts.	1	≥1.2	Maintain dose level	Maintain dose level
	2	1.0 to <1.2	Maintain dose level	Maintain dose level
	3	0.5 to <1.0	Reduce 1 dose level	Maintain dose level

**Table 6-14: Dose modification for hematological toxicity**

Prior to Dosing (Day 1 or Day 15)	Toxicity		Dose level for subsequent cycles	
	CTCAE (V5.0) Toxicity Grade	Platelets ( $\times 10^9/L$ )	Oxaliplatin	5-Fluorouracil
If ANC is $\geq 1.2$ within 2 weeks, proceed with treatment at a dose level according to the lowest ANC result of the delayed weeks.	4	<0.5	Reduce 1 dose level	Omit iv bolus and reduce infusion 1 dose level
If ANC remains <1.2 after 2 weeks, discontinue treatment.				
If platelets <75 on Day 1 or Day 15, hold treatment. Perform weekly blood counts.	1	$\geq 75$	Maintain dose level	Maintain dose level
If platelets $\geq 75$ within 2 weeks, proceed with treatment at a dose level according to the lowest platelets result of the delayed weeks.	2	50 to <70	Maintain dose level	Maintain dose level
If platelets remain <75 after 2 weeks, discontinue treatment.	3	10 to <50	Reduce 1 dose level	Maintain dose level
	4	<10	Reduce 2 dose levels	Maintain dose level

ANC=absolute neutrophil count; CTCAE= Common Terminology Criteria for Adverse Events; iv=intravenous(ly)

#### 6.6.3.4.3 Dose modifications for non-hematological, non-neurological toxicity

Recommended dose modifications for non-hematological, non-neurological toxicity are outlined in [Table 6-15](#). Along with dose modifications, supportive treatment should be initiated per institutional guidelines.

**Table 6-15: Dose modification for non-hematological, non-neurological toxicity**

Prior to Dosing (Day 1 or Day 15)	Toxicity		Dose level for subsequent cycles	
	CTCAE (V5.0) Toxicity Grade	Diarrhea	Oxaliplatin	5-Fluorouracil
If diarrhea $\geq 2$ on Day 1 or Day 15, hold treatment. Perform weekly assessments.	1	Increase of <4 stools/day, or mild increase in colostomy output	Maintain dose level	Maintain dose level
If diarrhea is <Grade 2 within 2 weeks, proceed with treatment at a dose level according to the highest Grade experienced.	2	Increase of 4 to 6 stools/day, or moderate increase in colostomy output; limiting instrumental ADL	Maintain dose level	Maintain dose level
	3	Increase of $\geq 7$ stools/day; hospitalization indicated; severe increase in	Maintain dose level	Reduce 1 dose level of iv bolus and infusion

